# 10.4 Reporting procedures

# 10.4.1 Adverse Event Reporting

# 10.4.2 Serious adverse event reporting

All deaths and immediately life-threatening events, whether related or unrelated, will be recorded in an SAE report and submitted to the IRB within 24 hours of site awareness. For other SAEs, [name] shall complete an SAE report and submit to the IRB as soon as possible, but in no event later than 10 working days after the he first learns of the effect.

[name]

# 10.4.3 Unanticipated problem reporting

[name] will be responsible for creating and completing a UP report form. Incidents that meet the OHRP criteria for UPs will be reported promptly on the following timeline:

- UPs that are SAEs will be reported to the IRB within 24 hours of the investigator becoming aware of the event.
- Any other UP will be reported to the IRB within 10 days of the investigator becoming aware of the problem.

The UP report will include the following information:

- Protocol identifying information: protocol title and number, PI's name, and the IRB project number;
- A detailed description of the event, incident, experience, or outcome;
- An explanation of the basis for determining that the event, incident, experience, or outcome represents an UP;
- A description of any changes to the protocol or other corrective actions that have been taken or are proposed in response to the UP.

### 10.4.4 Events of special interest

Events of special interest include documented hypoglycemia, probable hypoglycemia (symptoms reported by patient without hypoglycemia documented by blood glucose measurement) that required assistance from another person for treatment and incorrect recommendations given by the smartphone application.

## 10.4.5 Reporting of pregnancy

CHWs will ask women at risk of pregnancy (defined as premenopausal and without history of surgical sterilization) at each visit if they have reason to believe they could be pregnant. If a patient believes they could be pregnant, then a pregnancy test will be performed. If pregnancy test is positive, this patient will be referred for care through SLMH and withdrawn from the study. This will be reported to [name], who will subsequently report to the IRB.

Version #: 1.0
[name]

## 10.5 Study Halting Rules

Study suspension and revision of protocols will be considered if it appears that an inordinate number of severe adverse events are occurring. In particular, study suspension will be considered if there is an excessive incidence of severe hypoglycemia (documented BG <70 requiring emergency transfer and/or hospitalization). Estimates of the incidence of severe hypoglycemia with glibenclamide use vary, with one study reporting incidence of 7.4 episodes per 1000 person-years and another reporting 57.7 episodes per 1000 person-years (figure computed from study data). Given that we will enroll approximately 100 patients and follow them for 6-12 months, we will consider the occurrence of more than 3 episodes of severe hypoglycemia as warranting review of study protocols and consideration of study suspension.

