### 2.7 Potential Risk and Benefits to Subjects

### 2.7.1 Known Potential Risks

Immediate risks

- The potential immediate risks include the risks of taking metformin, glibenclamide, or aspirin, medications which have been in use for decades and have well-established safety and side-effect profiles.
  - Metformin: The most common side effect of metformin is gastrointestinal distress (e.g. dyspepsia, nausea, vomiting, diarrhea). This usually improves with time and most patients can tolerate these side effects, with only 5% of patients discontinuing the drug completely because of them^36. The most serious reported adverse effect of metformin is lactic acidosis. However, the incidence of this has been found repeatedly to be exceedingly low. In fact, a 2010 Cochrane review found no cases of lactic acidosis over 70,490 patient-years of metformin use, even when patients with some renal impairment were included. Finally, metformin can cause vitamin B12 deficiency with long term use
  - Glibenclamide: The primary potential adverse effect of glibenclamide is hypoglycemia. The proportion of patients taking glibenclamide who will suffer an episode of severe hypoglycemia (requiring the assistance of another for treatment and/or hospitalization) is estimated to be 0.5%
     Aspirin: Significant potential adverse effects of aspirin include gastrointestinal toxicity,
  - hemorrhage, renal toxicity, and hypersensitivity reactions
- Risk of errors in medication administration or recommendations due to user error or application
  malfunction
- Discomfort with finger sticks for blood glucose and hemoglobin A1c measurements

Long-range risks

• Complications of medication adverse effects (e.g. anemia from metformin or aspirin use, renal insufficiency as a related to aspirin use)

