## [name]

recommendations are given in every case), training of CHWs and physician oversight of application treatment recommendations and CHW decisions regarding medication administration and referrals.

Exit criteria for the study includes the following:

- Patient with eGFR <30 mL/min will be unable to safely take metformin or glibenclamide and thus will be
  excluded from the program. These patients will be referred to San Lucas Mission Hospital (SLMH) for
  consultation with [name] regarding alternate medication therapy.

- Women who are found to be pregnant during the study
- Patients who require insulin or additional medication other than metformin or glibenclamide for diabetes control

Patients with mild adverse effects, such as gastrointestinal upset from metformin or mild hypoglycemia or hypoglycemia symptoms on glibenclamide will have their medication adjusted according to the titration algorithms used by the application. Patients who are unable to tolerate metformin or glibenclamide due to adverse effects will be referred to [name] for assessment and further treatment recommendations. Patients with more severe adverse effects, such as severe hypoglycemia (defined as resulting in alteration in mental status and requiring assistance from a CHW) or hypoglycemia not responsive to initial measures in the field will be transferred to SLMH via ambulance for further care.

The program will pay the costs related to ambulance transfer to SLMH and the cost of treatment for medication adverse effects. Patients may incur costs from treatment for other complications of diabetes that fall outside the scope of the program, though this care is highly subsidized through the SLMH.

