## 4.1.3 Primary Safety Endpoints

- Documented hypoglycemia (blood glucose <70 mg/dL)

- Hypoglycemia requiring emergency transport to the hospital and/or hospitalization
- Instances in which the application provided an incorrect recommendation
- Patient death

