## 10.6 Safety Oversight

[name] will review all patient data each month to identify patient safety issues. Any issues will be promptly discussed with site investigator and medical director, [name], and with the PI, [name]. Special attention will be given to the following potential safety issues:

- Documented hypoglycemia. This includes those episodes requiring emergency patient transport (severe) and non-severe (those treated without complication in the field). While this is a known but side effect of glibenclamide, frequent occurrences in our patients may suggest the need for an alteration in our medication titration protocols
- Severe probable hypoglycemia (patient reports hypoglycemia symptoms that required the assistance of another person to treat due to altered mental status)
- Incorrect recommendations regarding medication dosing, management of complications, or recommendations for referral provided by the application
- AEs and UPs as described above, which would also be reported to the IRB.

Interim cumulative safety analysis will occur at 3 months, 6 months, and 9 months and final safety analysis at 12 months.

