# Appendix 4 - Hypoglycemia Protocol

# Protocol for identifying probable hypoglycemic episodes

- Patients who are taking glibenclamide are asked the following questions:
  - "In the last month, have you had episodes of any of the following symptoms":
    - Confusion
    - Trembling
    - Feeling uncoordinated
    - Palpitations
    - Abnormal sweating
    - Abnormal anxiousness
  - Patients reporting episodes of any of these symptoms are asked the following questions and their answers are scored as noted:
    - "Did these symptoms come on gradually or did they start suddenly"
      - Gradually (0)
      - Suddenly (+1)
    - "Did these symptoms occur when you had not eaten for several hours or after strenuous physical activity"
      - Yes (+1)
      - No (0)
    - "Did these symptoms improve after eating something
      - Yes (+1)
      - No (0)
- Patient considered to have probable hypoglycemia if above answers total to 2 or more points

and because the original validation study used this standard as well, we define adherence as taking medication "Nearly all of the time" or "All of the time".

<sup>10 Glibenclamide functions as an insulin secretagogue and has a duration of action of ~24 hours. Thus, it is expected to have a relatively short-term effect on blood glucose and it is essential to know the timing of the last dose when interpreting and acting on a patient's blood glucose level.

<sup>1These symptoms were found to be the most highly correlated with experimentally-induced hypoglycemia.

 <sup>12 In general, the onset of hypoglycemia symptoms is rapid rather than gradual
  This question assesses for the association of symptoms with two common risk factors for hypoglycemia that are likely to be present in our population

[name]

- Patients who have 2 or more points are asked the following question: "When you had these symptoms, were you so confused or sleepy that someone else needed to help you eat or drink something with sugar "
  - If YES, this is considered as an episode of probable severe hypoglycemia
  - If NO, this is considered an episode of probable mild hypoglycemia

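### Severe hypoglycemia is defined inconsistently, and the probable severe episodes that the application records are in neither the primary safety endpoints nor the Section 10.5 count

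*Combined protocol and SAP*

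**What the plan says.** The term carries different requirements in different sections:

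- **Sections 2.6 and 2.7.1** describe serious or severe episodes by the need for help or admission. Section 2.7.1 has "requiring the assistance of another for treatment and/or hospitalization". Both sections attach a 0.5% risk figure.
- **Section 2.7.2** has "defined as resulting in alteration in mental status and requiring assistance from a CHW".
- **Section 10.5** has "documented BG <70 requiring emergency transfer and/or hospitalization". More than 3 such episodes prompt a review of the protocols and consideration of suspension. Section 10.6 likewise labels documented episodes with emergency transport as severe.
- **Section 10.6** separately names severe probable hypoglycemia: "patient reports hypoglycemia symptoms that required the assistance of another person to treat due to altered mental status". No glucose reading is needed.

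Appendix 4 collects this last category. Patients on glibenclamide are asked about symptoms in the last month. Those scoring 2 or more points are asked whether they were so confused or sleepy that someone had to help them take sugar. "If YES, this is considered as an episode of probable severe hypoglycemia"

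Section 10.3 says that the application records assisted episodes, and Section 10.4.4 makes them events of special interest.

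The primary safety endpoints (Section 4.1.3, repeated in 10.1) are any documented glucose below 70 mg/dL, "Hypoglycemia requiring emergency transport to the hospital and/or hospitalization", incorrect application recommendations, and death.

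**The concern.** The safety of dose titration by CHWs is a stated secondary objective (Section 3). There is no formal DSMB (11.2.1) and no independent audit (11.1.1), so the Section 10.5 count is the only numerical safety trigger.

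An episode in which a confused patient is helped by a relative and recovers, with no reading and no transfer, is severe under Section 2.7.1 and probable severe under Appendix 4. It enters neither the primary safety endpoints nor the Section 10.5 count. The data would be in the database, but the headline safety table and the trigger would not show the episode. Because the definitions differ, a reported number of severe episodes would also be ambiguous unless the section it follows is stated.

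**Working it through.** **Step 1: apply each definition to the same episode.** The episodes are hypothetical; the criteria are the protocol's.

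| Episode | 2.7.1 | 2.7.2 | 4.1.3 / 10.1 | 10.5 count |
|---|---|---|---|---|
| Confused at home, relative gives sugar, recovers; no reading, no transfer | Severe | Not met (no CHW) | Not counted | Not counted |
| Confused at home, taken to hospital by ambulance, no reading below 70 obtained | Severe | Met only if a CHW helped | Counted on the wording of the transport endpoint | Not counted |
| Alert at a visit, glucose stays below 70 after treatment, transported | Depends on help or admission | Not met (mental status normal) | Counted | Counted |
| Alert at a visit, glucose below 70, corrects in the field | Not severe | Not met | Counted (any reading below 70) | Not counted |

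The definitions are not nested: the third episode counts under 10.5 but not under 2.7.2. Section 10.5 is the only one that states both a glucose reading and transfer or hospitalization. The first row is the gap.

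**Step 2: check the sentence in Section 10.3 on what is not an adverse event.** As written, it excludes symptoms without a documented low reading that did require another person's help. The following paragraph of Section 10.3 has such episodes recorded, and Section 10.4.4 makes them events of special interest. The exclusion reads as if a negative were missing. It also uses a cut-off of ≤70, where 4.1.3 and 10.5 use <70.

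**Step 3: look for the origin of the threshold.** Section 10.5 gives no formula for more than 3, so there is no derivation to reproduce. A consistency check uses its own inputs: about 100 patients, 6 to 12 months, and 7.4 or 57.7 episodes per 1000 person-years.

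Expected episodes m = patients × years × rate:

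- Low rate: 100 × 0.5 × 7.4/1000 = 0.37 at 6 months; 0.74 at 12 months.
- High rate: 100 × 0.5 × 57.7/1000 = 2.885 at 6 months; 5.77 at 12 months.

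The threshold is compatible with the high rate at 6 months, where 2.885 is close to 3.

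**Step 4: see how far the counted definition affects the trigger.** With a Poisson count, P(more than 3) = 1 − e^(−m)(1 + m + m²/2 + m³/6). For m = 2.885 this is 1 − 0.0559 × 12.05 = 0.327. The documents do not give the share of severe episodes that meet the Section 10.5 definition, so the shares below are assumed. They are applied to the high rate in 100 patients.

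| Share counted | m, 6 months | P(>3), 6 months | m, 12 months | P(>3), 12 months |
|---|---|---|---|---|
| 100% | 2.88 | 0.33 | 5.77 | 0.83 |
| 75% | 2.16 | 0.17 | 4.33 | 0.63 |
| 50% | 1.44 | 0.06 | 2.88 | 0.33 |
| 25% | 0.72 | 0.006 | 1.44 | 0.06 |

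The effect also runs the other way. If recalled episodes were added, the threshold stayed at more than 3, and the counted rate doubled to 115.4 per 1000 person-years, P(>3) at 6 months would rise from 0.33 to 0.83. Definition and threshold have to be set together.

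**The case against.** The strongest reply is that these episodes are already handled. Section 10.6 names them for special attention in the monthly review and adds cumulative safety analyses at 3, 6, 9 and 12 months. The trigger prompts review; it is not an automatic stop. Section 10.5 also covers any inordinate number of severe adverse events, and Section 5.7.1 allows suspension for unacceptable risk. The Appendix 4 episodes rest on one month's recall and a symptom score, so keeping them out of a hard count is defensible. All of this stands. It limits the consequence but does not remove the contradiction, and no count or threshold is attached to these episodes. The secondary endpoint on hypoglycemia symptoms (4.1.2) does not separate severe ones.

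Three stronger readings are tempting, and the documents do not support them:

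- A reader might infer that the primary safety endpoints use the narrowest definition. They do not. One counts any reading below 70, and the transport endpoint does not itself state that a reading is needed, although 10.3 and 10.6 treat transported episodes as a subset of documented ones.
- A reader might infer from monthly testing that most severe episodes will have no reading. Appendix 9 tells families to call an ambulance if the patient cannot eat or drink, and tells patients who needed help to seek care at once. Section 7.4.3 provides unscheduled assessments, and hospital records are reviewed (9.2.1, 10.3). The share with a reading is unknown.
- A reader might infer that the trial's rate will be flattered against the 0.5% figure. No section plans that comparison. Section 10.5 uses 7.4 and 57.7 per 1000 person-years, and the case definitions behind those rates are not given, so a mismatch cannot be checked.

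**Conclusion.** The concern holds in a limited form. Severe hypoglycemia is defined inconsistently across Sections 2.6/2.7.1, 2.7.2 and 10.5/10.6. Assisted episodes without a reading or transfer are recorded and reviewed monthly, but they are absent from the primary safety endpoints and from the only numerical trigger, so both can miss severe episodes treated at home.

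The number missed cannot be estimated from the documents. The probabilities above (0.33 falling to 0.06 at 6 months, and 0.83 falling to 0.33 at 12 months, when half of the episodes count) show sensitivity only. They assume 100 patients, Poisson counts, the upper published rate and an assumed share. That rate also applies to glibenclamide users, whereas Section 10.5 sets it against all of the roughly 100 patients. If 30% to 70% took glibenclamide (assumed), the high-rate expectation would fall to 0.9–2.0 at 6 months and 1.7–4.0 at 12 months.

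This should be corrected, but it does not undermine the design.

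**What to change.** 1. Reconcile the definitions across Sections 2.6, 2.7.1, 2.7.2, 4.1.3/10.1, 10.5 and 10.6. Include the adverse-event exclusion in 10.3, which conflicts with the rest of 10.3 and with 10.4.4. The sponsor decides which definition applies.
2. List application-recorded probable severe hypoglycemia (Appendix 4) as a safety endpoint in 4.1.3 and 10.1.
3. In the review that informs Section 10.5, report documented severe and probable severe counts separately and together.
4. If the definition counted in Section 10.5 changes, re-derive the threshold of more than 3 on that definition, and state the rate, the number of patients at risk and the follow-up assumed.

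No new data collection is needed. Items 1 to 3 change wording and tabulation. Item 4 needs a short calculation, and a changed count would change how the trigger operates. The drawback is that recalled episodes are less certain than documented ones, which is why the counts should also be shown apart.

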## 10.6 Safety Oversight

[name] will review all patient data each month to identify patient safety issues. Any issues will be promptly discussed with site investigator and medical director, [name], and with the PI, [name]. Special attention will be given to the following potential safety issues:

- Documented hypoglycemia. This includes those episodes requiring emergency patient transport (severe) and non-severe (those treated without complication in the field). While this is a known but side effect of glibenclamide, frequent occurrences in our patients may suggest the need for an alteration in our medication titration protocols
- Severe probable hypoglycemia (patient reports hypoglycemia symptoms that required the assistance of another person to treat due to altered mental status)
- Incorrect recommendations regarding medication dosing, management of complications, or recommendations for referral provided by the application
- AEs and UPs as described above, which would also be reported to the IRB.

Interim cumulative safety analysis will occur at 3 months, 6 months, and 9 months and final safety analysis at 12 months.

#### 10.7 Unblinding Procedure

Not applicable

# 11 Study Monitoring, Auditing, and Inspecting

#### 11.1 Medical Monitoring

#### 11.1.1 Study Monitoring Plan

Clinical site monitoring is conducted to ensure that the rights and well-being of human subjects are protected, that the reported trial data are accurate, complete, and verifiable, and that the conduct of the trial is in compliance with the currently approved protocol/amendment(s), with GCP, and with applicable regulatory requirement(s).

- [name] will perform both remote monitoring once per month and in-person monitoring at several
  points during the study. In-person monitoring will occur early in the study during the enrollment process
  to assist with CHW training and study logistics. He will again visit between 6 and 12 months postenrollment for data analysis and program evaluation and improvement. Monitoring will be targeted on
  clinical endpoints, adverse effects, identified complications of diabetes, and accuracy of application
  recommendations and CHW actions
- Independent audits will not be conducted

Version #: 1.0

[name]

## 11.2 Protocol Deviations

A protocol deviation is any noncompliance with the clinical trial protocol, GCP, or MOP requirements. The noncompliance may be either on the part of the participant, the investigator, or the study site staff. As a result of deviations, corrective actions are to be developed by the site and implemented promptly. These practices are consistent with ICH E6:

- 4.5 Compliance with Protocol, sections 4.5.1, 4.5.2, and 4.5.3
- 5.1 Quality Assurance and Quality Control, section 5.1.1
- 5.20 Noncompliance, sections 5.20.1, and 5.20.2.

The site PI/co-investigator/staff will be responsible for continuous vigilance to identify and report deviations to the protocol. These will be reported within 14 working days of identification of the protocol deviation, or within 14 working days of the scheduled protocol-required activity. All deviations must be addressed in study source documents, reported to the IRB. Protocol deviations will be sent to the local IRB per their guidelines. The site PI/study staff is responsible for knowing and adhering to their IRB requirements. Further details about the handling of protocol deviations will be included in the MOP.

#### 11.2.1 Internal Data and Safety Monitoring Board

There will be no formal DSMB. Study will be monitored as described in 11.1.1 and 10.6 and safety issues will be reported to the IRB.

# 11.3 Auditing and Inspecting

The investigator will permit study-related monitoring, audits, and inspections by the IRB (or their representatives) of all study related documents (e.g. source documents, regulatory documents, data collection instruments, study data etc.). The investigator will ensure the capability for inspections of applicable study-related facilities (e.g. pharmacy, diagnostic laboratory, etc.).

#### 11.4 Subject Compliance Monitoring

At each visit, CHWs will assess medication compliance via patient report (see Appendix 3). Compliance with medication for diabetes is accounted for in treatment protocols and titration of medications. For patients who are noncompliant, CHWs will emphasize the importance of compliance to the patient and work with the patient to improve compliance. Patients will not be withdrawn from the study for repeated noncompliance, as this would deny them diabetes treatment and decrease the real-world applicability of our findings. Nonadherence with diabetes medications is common, with studies suggesting that only 50-75% of patients take more than 80% of their medication doses.

